2.2.2 Other secondary objectives

- To assess the effect of LCZ696, compared to enalapril, on reducing the rate of the composite endpoint of CV death and total (first and recurrent) HF hospitalizations
- To assess the effect of LCZ696, compared to enalapril, on the clinical composite score (as assessed by NYHA classification and patient global assessment) at predefined time point (Month 6)
- To assess the effect of LCZ696, compared to enalapril, on delaying the time to all-cause mortality
- To assess the effects of LCZ696, compared to enalapril, on reducing the number of patients hospitalized and number of hospital admission (all-cause and cause-specific)
- To assess the effects of LCZ696, compared to enalapril, on reducing healthcare resource utilization, e.g., number of days/stays in ICU, number of rehospitalizations, and number of ER visits for HF
- To assess the effects of LCZ696 and enalapril on changes in pre-specified and/or other relevant biomarkers (e.g., cardiac, vascular, renal, collagen, metabolism, and inflammatory biomarkers) from baseline to predefined timepoints (Weeks 2, 4, 8, Month 6 and 18)

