3.1.1.2 Single-blind active treatment run-in epoch

Patients who are successfully screened into the study at Visit 1 will enter the single-blind active treatment run-in epoch. Since this epoch will be a single-blind period, the site staff working with patients should exercise caution when discussing the study procedures and the study drug with patients to keep the patient blinded to the identity of the study drug.

Please refer to [Table 6-1](#) for a detailed list of study procedures and assessment to be performed at each run-in epoch visit.

Visit 101

Once patients' eligibility has been ascertained, they will attend Visit 101 approximately one to two weeks after Visit 1 to start LCZ696 50 mg b.i.d. for 2 weeks. Patients should continue to take their background medications for CHF, with the exception of ACEIs or ARBs which must be discontinued at Visit 101.

If patients meet the criteria in [Table 3-1](#), they will start to take the LCZ696 50 mg b.i.d. run-in medication the day after Visit 101. An approximately 36-48 hour wash-out period stopping concomitant ACEIs or ARBs should be included before the enrolled patients start taking the first dose of LCZ696. For example, if a patient's Visit 101 is on Wednesday, he/she must not take any doses of ACEIs or ARBs after the last dose on Tuesday. The patient will then start taking the first dose of LCZ696 50 mg b.i.d. run-in medication on Thursday morning.

End of treatment run-in visit (Visit 199)

A Visit 199 (end of treatment run-in visit) will be completed for all patients who enter the treatment run-in epoch. Patients not tolerating LCZ696 50 mg b.i.d. ([Table 3-1](#)) will be considered run-in failures and withdrawn from the study. For patients who discontinue during the treatment run-in epoch, Visit 199 will be their discontinuation visit.

Only patients who tolerate LCZ696 50 mg b.i.d. for 2 weeks will be eligible for randomization. For patients that are eligible to be randomized, Visit 199 will be their end of treatment run-in disposition visit and may be performed on the same day as Visit 201. [Table 6-1](#) lists all procedures to be performed at Visit 199.

Safety and tolerability monitoring during the active treatment run-in epoch

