3.1.1.3 Double-blinded randomized treatment epoch

The randomized treatment epoch will begin at Visit 201. Patients who successfully complete the run-in and tolerate LCZ696 50 mg b.i.d. will be randomized to receive LCZ696 100 mg b.i.d. or enalapril 5 mg b.i.d. for 4 weeks and be up-titrated to the target dose of LCZ696 200 mg b.i.d. or enalapril 10 mg b.i.d. in a 1:1 ratio in a double-blind manner. Please refer to [Table 6-1](#) for a detailed list of study procedures and assessment to be performed at each randomized treatment epoch visit.

The study medication will be added to the prescribed background HF therapy. Concomitant administration of ACEIs or ARBs with the study medication is strictly prohibited. Please refer to [Section 5.5.7](#) for more information on co-administration of other medications.

Reported trial outcome endpoint events will be collected as they occur throughout the randomized treatment epoch. All laboratory evaluations for planned visits after randomization

will be performed through the central laboratory or other authorized laboratory. Unscheduled laboratory assessments can be performed locally as necessary.

Visit 201 will be considered the reference visit for all study visits during the randomized treatment epoch. Regardless of the occurrence of any unscheduled visits, scheduled visits should occur within the timeframe in relation to Visit 201 as outlined in [Table 6-1](#).

Randomization Visit (Visit 201)

Patients who have met all the inclusion criteria and none of the exclusion criteria at the end of the active treatment run-in epoch will be randomized to either LCZ696 100 mg b.i.d. or enalapril 5 mg b.i.d. in a 1:1 ratio.

Site personnel should instruct the patient to refrain from taking their run-in medication on the day of Visit 201. Site personnel will document the date and time of the last dose of the LCZ696 run-in medication. This is necessary to ensure a 36-hour wash-out period to avoid overlapping of LCZ696 with enalapril and minimize the potential risk of occurrence of angioedema.

If appropriate, the patient will start to take the double-blind study medication (LCZ696 100 mg b.i.d. or enalapril 5 mg b.i.d.) the day after Visit 201. For example, if a patient's Visit 201 is on Wednesday, he/she must not take any doses of the LCZ696 50 mg b.i.d. run-in medication after Tuesday evening. The patient will then start taking the first dose of the double-blind study medication on Thursday morning.

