⁹ Serum potassium and eGFR (estimated by using serum creatinine value).

¹⁰ Complete laboratory evaluations (hematology, blood chemistry, and urine) will be collected in the fasting state and sent to the central laboratory.

¹¹ Abbreviated chemistry panel including serum potassium, blood urea nitrogen (BUN), and serum creatinine will be measured at interim visits at the central laboratory.

¹² Women of childbearing potential only. At Visit 1, 299 and in case of a positive urine pregnancy result, a confirmatory serum pregnancy test has to be performed at the central laboratory. A Urine pregnancy test will be performed locally at Visit 199, 205 and every 4 months up until Visit 299 (except for Visit 299). If positive with serum /urine pregnancy test during the screening or treatment run-in epoch, the patient must be discontinued from the trial. After randomization (Visit 201) a positive pregnancy test requires immediate interruption of study drug.

¹³ Run-in disposition page to be completed for all patients who entered into the treatment run-in epoch.

¹⁴ Screening ECG performed within the 6 months before Visit 1 is accepted.

¹⁵ Procedure completed only for patients to be randomized at Visit 201

¹⁶ At Visit 202, plasma sample for biomarkers such as NT-proBNP will be collected. At Visit 209, serum sample for selected biomarkers related to fibrosis/remodeling will be collected.

Table 6-2 Assessment schedule (OLE epoch)

Epoch	DS/S	Open-label extension									
		301 [†]	302	303	304	305	306	307	308	UNS [°]	399 ^{††} (EOS/ ITD)
Visit	DS/S	0w	2 to 4w	8w	4m	8m	12m	16m	20m	-	EOS ^{††}
Weeks (w) / Months (m)											
Informed consent form	S	x									
Call to IRT ¹	DS	x	x	x	x	x	x	x	x	x	x
Inclusion/Exclusion criteria	DS	x									
Concomitant medications	DS	x	x	x	x	x	x	x	x	x	x
Physical Exam ²	S	x ¹⁰	x	x	x	x	x	x	x	x	x
Vital signs (BP and pulse)	DS	x ¹⁰	x	x	x	x	x	x	x	x	x
Weight	DS	x ¹⁰	x	x	x	x	x	x	x	x	x
NYHA Classification (HF signs and symptoms)	DS	x ¹⁰	x	x	x	x	x	x	x		x
Echocardiography ³	DS	x					x				
12-lead ECG evaluation	DS	x ¹⁰					x			(x)	x
Complete laboratory assessments ⁴	DS	x ¹⁰			x		x			(x)	x
Abbreviated chemistry panel ⁵	DS		x	x		x		x	x	(x)	
Local laboratory assessments ⁶	S	x	x								
Pregnancy tests (Serum / Urine) ⁷	DS	x			x	x	x	x	x	(x)	x
Plasma / Urine biomarkers ⁸	DS	x	x	x	x		x				
AEs / SAEs	DS	x	x	x	x	x	x	x	x	x	x
Extension medication dispensation	S	x	x	x	x	x	x	x	x	(x)	
Drug accountability	S		x	x	x	x	x	x	x	(x)	x

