6.4.4 Biomarkers

Biomarkers related to cardiac and renal function/injury and associated comorbidities and their consequences in the HF-rEF population will be obtained from blood and first morning void (FMV) urine. Biomarkers will be used to elucidate the effect of study drugs. They may also be

used to determine which biomarkers are most predictive of event risk. Blood biomarkers of potential interest may include such as: NT-proBNP, aldosterone, Cystatin-C, high-sensitivity troponin T, amino-terminal propeptide of procollagen type I (PINP) and type III (PIIINP) or other biomarkers important in heart failure. FMV urine biomarkers may include markers such as cGMP, creatinine, and urine albumin to creatinine ratio (UACR). The list of blood and urine biomarkers may change during the course of the study as new or more relevant biomarkers are determined. Biomarker analysis may also occur retrospectively after study close with biomarker decisions dependent on study outcome and/or new biomarkers relevant to the HF-rEF patient population.

In the core part, NT-proBNP will be obtained in all patients by using a central laboratory at Visit 1 to determine eligibility for the trial. In addition, biomarker measurements will be obtained from serum, plasma, and first morning void (FMV) urine samples at Visits 101, 199, 202 (only selected biomarkers such as NT-proBNP), 203, 204, 206 and 209 (only selected biomarkers at Visit 209) to determine effects of treatments on biomarkers. Biomarkers related to fibrosis/remodeling such as PINP and PIIINP will be measured only at Visits 101 and 209. Values of selected biomarkers at Visit 101 may also be used to determine which biomarker best predicts risk of clinical events.

In the OLE, biomarker measurements will be obtained from plasma and spot urine samples at Visits 301, 302, 303, 304, and 306 to determine effects of LCZ696 treatments on biomarkers. BNP, NT-proBNP, and urine cGMP at these visits will be assessed.

These samples will be obtained before patients take their morning study drug dose.

The results of the biomarkers analyzed during the conduct of the core part, with the exception of the Visit 1 NT-proBNP results, will be blinded to the site and the Novartis clinical study team until the core part database lock. The Novartis clinical study team will only be unblinded to biomarker data following the core part database lock.

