9.5.1.10 Biomarkers

In the core part, for the treatment comparisons of LCZ696 vs enalapril, change from baseline (Visit 101) to the pre-defined time-points in logarithmic scale will be analyzed using a repeated measures ANCOVA model with treatment, the stratification factor screening NT-proBNP, visit and treatment-by-visit interaction as fixed effect factors and the logarithmic baseline biomarker value as a covariate, with a common unstructured covariance matrix among visits for each treatment. The estimated treatment effects in terms of ratios of geometric means, based on the least-squared means for within and between treatment groups from the ANCOVA model, and the corresponding two-sided 95% confidence intervals will be provided. The analysis will be performed based on all available data in the FAS and based on likelihood method with an assumption of missing at random for missing data. Descriptive

summary statistics (mean, median, standard deviation, min, max, Q1, Q3, geometric mean, 95% CI for geometric mean) for the change from Visit 101 to each post-baseline visit will be presented. Graphical mean plots with 95% CIs will also be provided.

Analysis will be conducted for all of the FAS population with relevant biomarker measures.

To characterize the effect of the two LCZ696 dosages (100 mg b.i.d., 200 mg b.i.d.) on NT-proBNP, the estimates of ratio from baseline (Visit 101) at Week 4 and Week 8 of LCZ696 treatment arm from the ANCOVA model described above are presented, and comparison of change from baseline at each dose level will be made using a t-test. Descriptive summary statistics for the changes from Visit 199 to post-randomization visits (Visits 202, 203, 204, 206) will be presented for LCZ696 treatment arm. In addition, descriptive summary for the change from Visit 199 to Visit 206 (Month 6) will be summarized by actual dose level immediately prior to Visit 206 for LCZ696 treatment arm. Graphical mean plots with 95% CIs will be provided as well. Analysis will be conducted for all of the FAS population with NT-proBNP measures. Same analysis will be conducted for the patients who did not require any dose adjustment(s) up to Week 8 in the FAS population with NT-proBNP measures. Analysis described above will be repeated for the subgroups, defined by the stratification for randomization – screening NT-proBNP (< 1,600 pg/mL, \geq 1,600 pg/mL).

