For reference, same analysis will be performed for enalapril treatment arm to characterize the effects of enalapril dosages (5 mg b.i.d., 10 mg b.i.d.).

In the OLE epoch, for biomarkers, descriptive summary statistics (mean, median, standard deviation, min, max, Q1, Q3, geometric mean, 95% CI for geometric mean) for the change from baseline (Visit 301) to each post-baseline visit will be presented. FAS-Ext will be used, and analyses will be done by the treatment arm in the double-blind treatment epoch. Additionally, analyses in NT-proBNP will be repeated for subset of FAS-Ext with only patients in the LCZ arm of the double blind treatment epoch, throughout the period from run-in epoch to OLE epoch biomarker visits (Visits 301, 302, 303, 304 and 306) using Visit 101 as baseline.

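### The between-arm biomarker model adjusts only for Visit 101 and ignores the pre-randomization Visit 199 value, leaving a modest gain in precision unused

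*Protocol*

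**What the plan says.** Protocol section 9.5.1.10 specifies the between-arm analysis in full. The outcome is the log-scale change from Visit 101. The fixed effects are treatment, the two-level screening NT-proBNP stratum, visit and treatment-by-visit. The remaining terms are "the logarithmic baseline biomarker value as a covariate, with a common unstructured covariance matrix among visits for each treatment". Results are ratios of geometric means with two-sided 95% confidence intervals.

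A second pre-randomization sample exists. Section 6.4.4 states that "biomarker measurements will be obtained from serum, plasma, and first morning void (FMV) urine samples at Visits 101, 199, 202" and later visits. Section 3.1.1.2 places Visit 199 at the end of the LCZ696 run-in that every patient receives: "Visit 199 will be their end of treatment run-in disposition visit and may be performed on the same day as Visit 201". Under section 3.1.1.3, "the patient will start to take the double-blind study medication (LCZ696 100 mg b.i.d. or enalapril 5 mg b.i.d.) the day after Visit 201".

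The only stated uses of Visit 199 values in section 9.5.1.10 are within-arm. "Descriptive summary statistics for the changes from Visit 199 to post-randomization visits (Visits 202, 203, 204, 206) will be presented for LCZ696 treatment arm", followed by a Month 6 summary by dose level. "For reference, same analysis will be performed for enalapril treatment arm to characterize the effects of enalapril dosages".

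**The concern.** A value measured before the first randomized dose cannot be affected by the assigned arm. Adjusting for it therefore leaves the between-arm comparison unchanged in meaning and removes residual variance. Visit 199 is also two weeks closer to the post-randomization visits than Visit 101, so under decaying correlation it should be the better predictor of Weeks 4 and 8. The model leaves it out.

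The stake is the width of the confidence interval for the LCZ696/enalapril ratio. This model serves the other secondary objective in section 2.2.2: "To assess the effects of LCZ696 and enalapril on changes in pre-specified and/or other relevant biomarkers". The first key secondary objective (section 2.2.1) is worded around the two LCZ696 doses and not against enalapril; its within-arm comparison of Week 8 with Week 4 gains essentially nothing. With about 220 patients, a number set mainly by feasibility (section 9.7), precision cannot easily be bought by recruiting more.

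**Working it through.** **The plan's own figure.** The protocol gives no precision or power figure for biomarkers. Its only sizing figure is 57 events for an 80% chance of an observed hazard ratio below 1. It reproduces: 4 × (0.8416 / ln 0.80)² = 56.9. It does not depend on the biomarker model.

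**Inputs from the protocol.** 220 patients, 1:1; stratum from Visit 1 NT-proBNP cut at 1,600 pg/mL; Visit 101 about two weeks before randomization and Visit 199 at about week 0; NT-proBNP measured at Weeks 2, 4 and 8 and Month 6. The Week 2 sample comes from the note to Table 6-1: "At Visit 202, plasma sample for biomarkers such as NT-proBNP will be collected".

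**Inputs assumed.** All between-visit correlations.

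**Hand check, leaving the stratum aside.** On a standardized scale, let r₁ and r₂ be the correlations of Visit 101 and Visit 199 with a later visit, and r₁₂ their correlation with each other.

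- Residual variance with Visit 101 only: 1 − r₁²
- With both: 1 − (r₁² + r₂² − 2r₁r₂r₁₂) / (1 − r₁₂²)

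Take a correlation of 0.9·exp(−0.02 × lag in weeks), so r₁₂ = 0.865:

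| Visit | r₁ | r₂ | Visit 101 only | Both | Variance ratio | SE change |
|---|---|---|---|---|---|---|
| Week 4 | 0.798 | 0.831 | 0.363 | 0.285 | 0.784 | −11.4% |
| Week 8 | 0.737 | 0.767 | 0.457 | 0.390 | 0.854 | −7.6% |
| Month 6 | 0.514 | 0.535 | 0.736 | 0.703 | 0.956 | −2.2% |

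With the stratum in the model (cut at the median), the SE changes are −10.8%, −7.0% and −2.1%.

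**Contribution of Visit 199 across correlation patterns, stratum included.**

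- Decaying correlation (0.75–0.95 at short lag, decay 0.01–0.05 per week): SE falls about 8–13% at Week 4, 6–8% at Week 8 and 1–4% at Month 6. That equals about 17–31%, 13–18% and 1–7% more patients.
- Constant correlation of 0.6–0.9: SE falls about 5–10% at every visit, so the gain is then not concentrated at Weeks 4–8.

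**Full model against the planned model.** Large-sample variance of the arm contrast, with correlation R·(a + (1−a)·exp(−lag/τ)). The main grid has 576 cases: R 0.85–0.95, a 0.3–0.85, τ 6–52 weeks, all Visit 199 correlations multiplied by 0.85–1, stratum share 0.3–0.6.

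| Added to the plan | Week 4 | Week 8 | Month 6 |
|---|---|---|---|
| Visit 199, by-visit slopes for both | −4.8 to −23.4% | −3.3 to −19.0% | −3.1 to −13.4% |
| Visit 199, one common slope each | −4.7 to −23.4% | −2.5 to −19.0% | −13.0 to +4.8% |

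SE is the square root of variance, so the first row is about 2.4–12.5%, 1.7–10.0% and 1.6–6.9% of interval width. At Month 6, 0.3–9.2 points of the cut come from Visit 101-by-visit alone; Visit 199 itself adds 0.6–13.1%. Under stronger decay (480 cases; a 0–0.3, τ 6–26), a common slope at Month 6 runs from −1.3% to +11.7%. This is why by-visit slopes are needed.

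**Unfavorable case.** Lowering only Visit 199's correlations with later visits (852 cases), the cut reaches 0.0% at Weeks 4 and 8. Where its Week 4 correlation is at least 0.05 below Visit 101's, the median cut is 1.0–1.4% at Week 4 and 0.8–0.9% at Week 8.

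**Simulation at n = 220.** 1,500 runs, 5% of Visit 199 values missing and filled treatment-blind, by-visit slopes; change in empirical variance:

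| Scenario | Week 4 | Week 8 | Month 6 |
|---|---|---|---|
| Moderate | −9.6% | −6.0% | −6.3% |
| Strong decay | −18.8% | −11.1% | −9.1% |
| Visit 199 clearly worse than Visit 101 | −0.9% | −1.0% | −2.4% |
| Visit 199 weaker in the enalapril arm only (× 0.85) | −3.7% | −1.8% | −5.8% |

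Coverage was 93.5–96.1% and bias at most 0.004 SD.

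**The case against.** The planned model is valid, Visit 101 is legitimately named as its baseline under the exception in section 9.2, and no decision rests on this interval. All of that stands, and it is why the point is only a suggestion. It is not simply a detail for the SAP, because section 9.5.1.10 already writes out the covariates.

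The benefit also depends on unknown correlations, and there is a reason for doubt. Visit 101 follows stable ACEI or ARB therapy, Visit 199 follows two weeks of LCZ696, and the enalapril arm then leaves LCZ696. Visit 199 may predict less well in that arm. In the simulation of that case the SE gain is only about 1.9%, 0.9% and 2.9% at Week 4, Week 8 and Month 6. This objection stands as a limit on size.

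That by-visit slopes never lost precision in the grids proves little: large-sample variance cannot rise when covariates with visit-specific slopes are added. Only the simulations bear on finite-sample cost, and the four scenarios above showed no loss.

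Finally, the calculations model a marker whose own screening value defines the stratum, that is NT-proBNP. No size is shown for the other biomarkers. The change also needs a rule for missing Visit 199 values in an analysis that otherwise relies on likelihood under missing at random.

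**Conclusion.** The point holds as a minor matter of efficiency. The protocol collects a second pre-randomization biomarker value and leaves it out of the between-arm model. For NT-proBNP under time-decaying correlations, using it with by-visit slopes cuts the contrast variance by roughly 5–23% at Week 4, 3–19% at Week 8 and 3–13% at Month 6. The gain is near zero at Weeks 4 and 8 if Visit 199 predicts clearly worse than Visit 101. These figures rest on assumed correlations. Nothing here is a bias, an error or a contradiction, and neither the primary analysis nor any success threshold is affected.

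**What to change.** In section 9.5.1.10, for biomarkers measured at both Visit 101 and Visit 199:

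- Add log Visit 199 as a second covariate, with covariate-by-visit interactions for both log Visit 101 and log Visit 199. Do not use a single common slope.
- Keep change from Visit 101 as the outcome, and take least-squares means at the overall covariate means.
- Fill a missing Visit 199 value by a treatment-blind rule using pre-randomization data only, for example a pooled prediction from log Visit 101 and the stratum, so that no patient is dropped.
- Leave PINP and PIIINP as they are; they are measured only at Visits 101 and 209.

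This needs no new samples or procedures. For NT-proBNP at four visits there are 2 × 4 = 8 covariate slopes instead of 1, so 7 more parameters, or about one degree of freedom per visit contrast. Apart from Visit 1 NT-proBNP, biomarker results are withheld from sites and the clinical study team until the core database lock (section 6.4.4), so the change can be fixed before then without sight of the data.

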9.5.2 Safety variables

The safety and tolerability assessments are listed below:

- AEs and SAEs
- Sitting systolic, diastolic BP, and pulse pressure
- Heart rate
- Symptomatic hypotension and/or SBP < 90 mmHg
- Angioedema
- Hyperkalemia
- Renal dysfunction
- Cough
- Drug-related hepatic disorders
- Other relevant laboratory values
- ECG changes

The assessment of safety will be based primarily on the frequency of adverse events, SAEs, and laboratory abnormalities. Other safety data will be summarized as appropriate.

The incidence of treatment-emergent adverse events (new or worsened) will be summarized by primary system organ class, preferred term, severity, and relationship to study drug. In addition, the incidence of death, SAEs, and AEs leading to discontinuation will be summarized separately by primary system organ class and preferred term.

Laboratory data will be summarized by presenting shift tables using extended normal ranges (baseline to most extreme post-baseline value), by presenting summary statistics of raw data and change from baseline values (mean, medians, standard deviations, ranges) and by the flagging of notable values in data listings.

Data from other tests (e.g., ECG or vital signs) will be listed, notable values will be flagged, and any other information collected will be listed as appropriate.

Safety analyses will be performed based on the safety population. There will be no formal statistical inference analysis.

In addition to the above safety analyses for the randomized double-blinded treatment epoch, the AEs, SAEs, and reasons for active run-in failures will be summarized for the active run-in epoch.

One cut-off data analysis will be carried during the OLE epoch after all patients have been enrolled into the OLE, and completed Visit 304 (Month 4) or discontinued.

The cut-off date is defined as the latest of Visit 304 date or discontinuation date (the last visit prior to Visit 304). All data on or prior to this cut-off date during the OLE epoch will be used for analysis. All specified safety analyses in this section will be performed for this cohort.

For AEs/SAEs, FAS-Ext will be used, and all analyses will be done for total, and by the treatment arm in the double-blind treatment epoch. Additionally, all analyses will be repeated for subset of FAS-Ext with only patients in LCZ arm of double blind treatment epoch, throughout the period from run-in epoch to OLE epoch.

Change from baseline (Visit 301) of lab parameters, vital signs and ECG will be summarized as given above. Shift from baseline of ECG data will be presented using shift table. FAS-Ext will be used, and all analyses will be done for total, and by the treatment arm in the double-blind treatment epoch. Additionally, all analyses will be repeated for subset of FAS-Ext with only patients in LCZ arm of double blind treatment epoch, throughout the period from run-in epoch to OLE epoch using Visit 201 as baseline.

[figure not shown]
Proportion of patients reaching target dose level 3 of LCZ696 at Week 8 and maintained at Month 4 will be presented. FAS-Ext will be used, and analyses will be done for total, and by the treatment arm in the double-blind treatment epoch.

